## Statistical Analysis Plan

### 2.1 Study objectives and endpoints

#### 2.1.1 Primary objective and endpoint

The primary objective of the study is:

- To evaluate the impact of afatinib therapy on the patient-reported lung cancer-specific symptom burden, using the Average Symptom Burden Index (ASBI) of LCSS in eligible patients, over 6 months of therapy, in a real world clinical setting in Greece.

The primary endpoint of the present study is:

- 6-month symptom improvement rate using the LCSS ASBI, i.e., proportion of patients who will experience a minimum clinically important improvement in symptoms (defined as a decrease in the ASBI from enrolment  $\geq 10$  in two consecutive assessments) over 6 months of treatment.

*Note: A patient will be categorized as having:*

- ✓ *an improved ASBI if the mean of any two consecutive post-baseline ASBI assessments for that patient is at least 10 points below the patient's ASBI at enrolment;*
- ✓ *a worsened ASBI if the mean of any two consecutive post-baseline ASBI assessments for that patient is at least 10 points above the value at enrolment;*
- ✓ *a stable ASBI if the mean of any two consecutive post-baseline ASBI assessments for that patient is within 10 points of the value at enrolment.*

*A change of 10 points on a 0-100 scale is considered sufficient to indicate a clinically meaningful change; this magnitude is about the same as the 0.5 standard deviation that has also reported as a universally acceptable minimum clinically important difference.*

#### 2.1.2 Secondary objectives and endpoints

The secondary objectives of the study are:

- To evaluate the effect of afatinib therapy on the patient-reported lung cancer-specific symptom burden, total symptomatic distress, functional activity status and global quality of life, using the LCSS total score and domain subscores, at the post-baseline predefined timepoints;
- To assess the impact of afatinib treatment on the HRQoL of the study population using the EuroQoL- 5 Dimensions- 3 Levels (EQ-5D-3L) questionnaire at the post baseline predefined timepoints;
- To assess the impact of afatinib therapy on patient's Eastern Cooperative Oncology Group Performance Status (ECOG PS) at the post baseline predefined timepoints;
- To record patient adherence to treatment with afatinib during the study observation period as well as the reasons for missing doses;

## Statistical Analysis Plan

- To assess the patterns of use of afatinib in routine clinical practice in terms of treatment modifications (permanent discontinuations, temporary interruptions, dose changes), and reasons for these modifications.

The secondary endpoints of the study, pertaining to secondary objectives are the following:

- Change in the total LCSS score, ASBI score and individual domain scores from enrolment to each post-baseline predefined timepoints; in addition change throughout the study observation period will be examined using longitudinal analysis;
- Proportion of patients (n, %) with reported problems for each level for each dimension of EQ-5D and proportion of patients with '*no problems*' (i.e., level 1) and '*with problems*' (i.e., level 2 & 3) at enrolment and at the post-baseline predefined timepoints;
- EQ-visual analogue scale (VAS) score (mean  $\pm$  SD) at enrolment and at the post-baseline predefined timepoints;
- Change in the proportion of patients in each of the EQ-5D dimension levels (no problems, with problems) and change in the EQ-VAS score between enrolment and post-baseline predefined timepoints;
- Change in ECOG PS scores from baseline to post-baseline predefined timepoints;
- Ratio of doses actually taken to doses prescribed over the study participation period and reasons for discrepancies;
- Proportions of patients with treatment discontinuations, temporary interruptions, or dose change(s) and reasons for treatment modifications.

### 2.2 Study variables

#### 2.2.1 Efficacy outcome (s)

##### 2.2.1.1 Primary outcome variable

- ASBI score of LCSS -*defined as the mean of the score of the 6 major lung cancer symptoms, i.e. loss of appetite, fatigue, cough, dyspnoea, pain, and haemoptysis-* at enrolment and at the 2-month intervals until the study visit at 6 months.

##### 2.2.1.2 Secondary outcome variables

- Patient-rated ASBI score of LCSS at the post-baseline predefined timepoints (*as defined in Section 3.2*);
- Patient-rated total LCSS score -*defined as the average of the aggregate score of all 9 items that comprise the LCSS-* at enrolment and at the post-baseline predefined timepoints;
- Patient-rated individual LCSS domain scores at enrolment and at the post-baseline predefined timepoints;

## ***Statistical Analysis Plan***

- Proportion of patients with reported problems for each level for each dimension of EQ-5D and proportion of patients with ‘no problems’ (i.e., level 1) and ‘with problems’ (i.e., level 2 & 3) at enrolment and at the post-baseline predefined timepoints;
- EQ-VAS score at enrolment and at the post-baseline predefined timepoints;
- ECOG PS score at baseline and at the post-baseline predefined timepoints;
- Ratio of doses actually taken to doses prescribed over the study participation period and reasons for discrepancies;
- Proportions of patients with treatment discontinuations, temporary interruptions, or dose modifications and reasons for treatment modifications.

## ***Statistical Analysis Plan***

### **2.2.2 Safety outcome(s)**

- ✓ Adverse event (AE) description;
- ✓ Onset date;
- ✓ End date;

## Statistical Analysis Plan

- ✓ Ongoing (yes, no);
- ✓ Causally related with GIOTRIF® (yes, no);
- ✓ Intensity according to National Cancer Institute (NCI) Common Terminology Criteria for Adverse Events (CTCAE) (Grade 1 or mild, Grade 2 or moderate, Grade 3 or high, Grade 4 or life-threatening, Grade 5 or death);
- ✓ Actions taken regarding GIOTRIF® for management of AE (none, dose reduction, permanent discontinuation, dose increase, completion of treatment according to protocol, treatment interruption and re-initiation, not applicable);
- ✓ Outcome (recovery, has not yet been recovered/ongoing, recovery with sequelae, death, unknown);
- ✓ Seriousness (yes, no).

### 2.3 Study design and conduct

This is a non-interventional, multicentre, cohort study, based on new data collection, which will include a representative sample of patients with advanced/metastatic NSCLC in Greece.

Patients will be treated according to the local prescribing information of the study medication (afatinib, GIOTRIF®) and routine medical practice in terms of visit frequency and types of assessments performed. The assignment of the patient to this therapeutic strategy is not decided in advance by the study protocol but falls within current practice and the prescription of afatinib is clearly separated from the physician's decision to include the patient in the current study.

[figure not shown]
Since this is purely non-interventional study, primary data -which will be obtained prospectively during the study visits through patients' interview and patient reported outcomes (PROs) or as performed per standard clinical practice- will mainly be employed.

Follow-up visit frequency will be determined by the treating physician, however study-related data will be collected at 2-month ( $\pm 3$  weeks) intervals during the first 12 months of study participation and every 6 months ( $\pm 3$  weeks) thereafter until the end of the study observation period.

A synoptic study diagram reflecting the assessments of interest and the suggested time schedule is presented in the following Figure 1:

## Statistical Analysis Plan

**Figure 1: Synoptic Study Diagram**

A total of 128 patients are planned to be enrolled by seven (7) Oncology and Pulmonology hospital centres/clinics in Greece specialized in lung cancer.

The overall study duration period is expected to be 60 months, including a 48-month enrolment period and a minimum 12-month follow-up period. During the observation period, data will be collected at routine clinical visits at 2-month intervals for the first 12 months and at 6-month intervals thereafter until the end of study participation.

In the context of this study which is planned to have an overall duration of 60 months, each participant will be treated with afatinib and observed in the context of the study until the end of study participation defined as a maximum of 48 months after afatinib treatment initiation or until disease progression, death, withdrawal of consent, unacceptable toxicity, study completion or physician's decision whichever occurs earlier. The maximum 48-month length of participation in the study pertains to the patients enrolled during the first 12 months of recruitment, while the maximum observation period for the last patient enrolled is 12 months.

Being non-interventional and observational in nature, this study does not impose any diagnostic/therapeutic interventions or strict visit schedule. Patients will be treated as per the routine medical practice in terms of visit frequency, types of assessments performed and with

[figure not shown]
## ***Statistical Analysis Plan***

adherence to the local prescribing requirements for afatinib. Investigators shall record all (S)AEs that are observed by them or reported by the patients. As this is an observational study, patients will continue to be followed by their physicians according to current medical practice and the product's summary of product characteristics (SmPC) requirements.

An assessment schedule in tabular format providing information on the recommended data collection schedule that most likely reflects the patterns of routine clinical care of most patients being treated with afatinib is depicted at Table 1.

***Statistical Analysis Plan***

***Statistical Analysis Plan***

## Statistical Analysis Plan

### 2.4 Determination of sample size

Sample size calculation has been based on study's primary endpoint, which involves the determination of the proportion of study population with clinically meaningful improvement in the LCSS ASBI score over a 6-month treatment period.

Due to the lack of published data on the effect of afatinib on symptom burden using the LCSS, the worst case scenario has been taken into account, i.e., that the proportion of patients experiencing symptom improvement (*as defined in Section 2.1.1*) after 6 months of therapy will be approximately 0.50. Consequently, the assessment of 96 patients is required to estimate the aforementioned proportion with a margin of error not exceeding 0.10 which represents a scientifically acceptable level of precision of the estimate [95% CI: 0.40-0.60;  $\alpha$ : 0.05; Relative Standard Error (RSE): 10.21%]. This means that for any proportion between 0.05 and 0.95, the precision will range from 0.04 to 0.10 at a 95% confidence limit. The sample size determination has been performed using the statistical software package SAS v9.4 (SAS Institute, Cary, NC).

In order to control for an estimated 25% drop out/non-evaluable rate, 128 patients are finally required in order to ensure the aforementioned sample size for the final statistical analysis.

## 3 DATA ANALYSIS CONSIDERATIONS

### 3.1 General presentation of summaries and analyses

Statistical analysis and generation of tables and patient data listings will be performed using SAS® statistical analysis software (the most updated version at the time of analysis onset). Figures will be created by validated graph programs, such as SAS® and/or Microsoft Excel.

Summary statistics will consist of frequency tables ( $n_{pt}$ , %) for categorical variables. For continuous variables, descriptive statistics [number of patients with available observations ( $n_{pt}$ ), number of missing observations ( $n_{miss}$ ), mean, standard deviation (SD), median, 25th and 75th percentiles, minimum (min) and maximum (max)] will be tabulated.

The normality of distribution of continuous variables will be examined using the Shapiro-Wilk test. Concerning binomial proportions 95% CIs will be derived from Wald confidence limits for binomial proportions. In order to examine the differences in the values of continuous variables, the paired t-test or the Wilcoxon signed-rank test for two dependent samples will be used. The association between categorical variables will be assessed with the use of the McNemar's test for paired samples.

Potentially, linear mixed-effects models for repeated-measures will be fitted in order to describe the trend of continuous variables over time. The impact of patient characteristics on variables of interest will be evaluated with the use of logistic regression models for dichotomous outcome variables. Pertaining to data presentation, when reporting relative frequencies or other percent values the following rules will apply:

- ✓ For values where all patients fulfil a certain criterion, the percent value will be displayed as 100.0.

## Statistical Analysis Plan

- ✓ For values where the absolute frequency is 0, ‘.’ will be presented instead.
- ✓ All other percent values will be displayed using one decimal place.

In terms of decimal places for descriptive statistics:

- ✓  $n_{pt}$ ,  $n_{miss}$  will be integers.
- ✓ Mean, SD, median, 25th percentile, 75th percentile, min and max will be rounded to one decimal place or to the minimum number of decimal places recorded in the eCRF plus one.

All statistical tests will be two-sided and will be performed at a 0.05 significance level. The exact p-values will be reported, even for non-significant results, rounded to 3 decimals unless the p-value is less than 0.001 or greater than 0.999 (in such cases  $p<0.001$  and  $p>0.999$  will be reported, respectively).

### 3.2 Analysis time points and assessment windows

The analysis time points of the study are the following:

- ✓ Enrolment/Baseline
- ✓ Post-baseline timepoints: At 2 months; 4 months; 6 months; 8 months; 10 months; 12 months; 18 months; 24 months; 30 months; 36 months; 42 months; 48 months post-afatinib treatment onset with a  $\pm 3$ -week window allowed;

### 3.3 Definition baseline and post-baseline values

In the context of this study the following definitions apply for the baseline and post-baseline assessments:

- ✓ **Baseline assessments:** are defined as the assessments performed prior to or at afatinib treatment onset. For PROs (EQ-5D-3L, LCSS) as well as for anthropometric characteristics, vital signs, and physical examination) data collected at the enrolment visit will serve as the baseline data.
- ✓ **Post-baseline predefined time points:** are defined as those performed at the post-baseline time points as defined in Section 3.2.

*Note: Data measured/collected at premature study withdrawal will also be considered as post-baseline values provided they have been collected within the predefined post-baseline time points.*

### 3.4 Protocol deviations/violations

Patients who will be considered as eligible for participation in this study must meet **all** the following inclusion criteria:

- ✓ Adult outpatients (18 years and older) of either gender;

## Statistical Analysis Plan

- ✓ Histologically or cytologically confirmed locally advanced or metastatic (IIIB/IV) NSCLC of any histological type with activating EGFR mutation(s) according to local laboratory EGFR testing;
- ✓ EGFR-TKI naïve patients;
- ✓ Patients for whom the decision to prescribe therapy with afatinib (GIOTRIF®) according to the locally approved product's SmPC has already been taken prior to their enrolment in the study and is clearly separated from the physician's decision to include the patient in the current study;
- ✓ Patients must be able and willing to provide written informed consent and to comply with the requirements of this study protocol;
- ✓ Patients must have signed an informed consent document;
- ✓ Patients must be able to read, understand and complete the study specific questionnaires.

A patient who meets **any** of the following criteria will be excluded from participation in this study:

- ✓ Patients who have initiated treatment with afatinib more than 7 days prior to their enrolment into the study;
- ✓ Patients that meet any of the contraindications to the administration of the study drug according to the approved SmPC;
- ✓ Patients currently receive treatment with any investigational drug/device/intervention or have received any investigational product within 1 month or 5 half-lives of the investigational agent (whichever is longer) before the commencement of therapy with afatinib.

### 3.5 Analysis sets

In accordance to the non-interventional design of the study, all statistical analyses will be performed in the Full Analysis Set (FAS) comprised of all eligible subjects who have been enrolled in the study, regardless of whether or not they have finally completed their projected participation in the study.

The analysis of the primary objective of the study will be performed in the Per Protocol Set (PPS) which will include all eligible study patients with available data pertaining to the study primary endpoint, i.e. 6-month symptom improvement rate as per the LCSS ASBI score. In case that the size of the PPS differs substantially (i.e.  $\geq 20\%$ ) from the size of the FAS, then descriptive statistics of demographic and baseline disease and clinical characteristics will also be presented in the PPS.

Subsets of FAS with available data will also be created and analysed for the purposes of secondary endpoint analyses. The safety analysis will also be applied in the FAS.

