### **11.8.1 Study populations**

In accordance to the non-interventional design of the study, all statistical analyses will be performed in the Full Analysis Set (FAS) comprised of all eligible subjects who have been enrolled into the study regardless of whether or not they have finally completed their projected participation in the study.

The analysis of the primary objective of the study will be performed in the Per Protocol Set (PPS) which will include all eligible study patients with available data pertaining to the study primary endpoint, i.e. 6-month symptom improvement rate as per LCSS ASBI score.

Subsets of patients with available data will also be created and analysed for the purposes of secondary endpoint analyses.

Patients erroneously enrolled in the study (i.e., not fulfilling the eligibility criteria) will be excluded from all analyses of this study and any deviations from the protocol will be reported in detail in the clinical study report (CSR).

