## Statistical Analysis Plan

Patients erroneously enrolled in the study (i.e., not fulfilling the eligibility criteria) will be excluded from all analyses of this study and any deviations from the protocol will be reported in detail in the clinical study report (CSR).

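### Safety is analysed in eligible enrolled patients rather than in all patients who took afatinib, so the safety tables can omit exposed patients and count undosed ones

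*SAP*

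**What the plan says.** SAP 3.5 sets the general population: "all statistical analyses will be performed in the Full Analysis Set (FAS) comprised of all eligible subjects who have been enrolled in the study". On safety it adds: "The safety analysis will also be applied in the FAS". The same section ends with the rule: "Patients erroneously enrolled in the study (i.e., not fulfilling the eligibility criteria) will be excluded from all analyses of this study". SAP 9 defines no set of its own and refers back to 3.5.

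Protocol 11.8.1 agrees. Its FAS is "comprised of all eligible subjects who have been enrolled into the study regardless of whether or not they have finally completed their projected participation", with the same exclusion of ineligible patients from all analyses. Protocol 11.8.5 summarises exposure in the FAS. Neither document defines a set of treated patients.

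Two eligibility criteria in SAP 3.4 matter most here. One exclusion criterion is: "Patients that meet any of the contraindications to the administration of the study drug according to the approved SmPC". One inclusion criterion requires that the decision to prescribe afatinib "has already been taken prior to their enrolment in the study"; it does not require that a dose has been taken.

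**The concern.** A safety summary is normally read as describing the patients who took the drug. Here membership depends on eligibility, which is a different property, and the two can part in both directions.

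- **Exposed but excluded.** Adverse reactions are collected from consent (Protocol 13.2, SAP 9.2), so they can be on file before a patient is found ineligible. Under the exclusion rule that patient then leaves the tables for adverse drug reactions (serious, non-serious and combined) and for serious adverse events, as well as the exposure-adjusted incidence rates (EAIRs). For a contraindication, the reason for exclusion may itself bear on risk.
- **Unexposed but included.** A patient who is eligible, consents and never starts afatinib stays in the denominators of the n (%) tables. Fatal events are collected from consent whatever their cause, so a death before the first dose could enter the serious adverse event table.

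At stake is whether the reported percentages and rates describe the afatinib-treated patients in this study.

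**Working it through.** **1. The plan's own denominator.** The only planned size is 96 evaluable and 128 enrolled (Protocol 11.6, SAP 2.4). It reproduces: 1.96² × 0.5 × 0.5 / 0.10² = 96.04, and 96 / (1 − 0.25) = 128. This point does not dispute it. The documents state no expected number of ineligible or undosed patients and no expected event rate, so everything below is assumed.

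**2. Exposed but ineligible patients.** Assume 128 treated patients, of whom x are ineligible, a serious adverse drug reaction (SADR) risk of 10% in eligible patients and r in ineligible ones. The plan reports 10% in expectation. The all-treated rate is [0.10 × (128 − x) + r × x] / 128.

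| x | r = 30% | r = 60% |
|---|---|---|
| 3 | (12.5 + 0.9)/128 = 10.5% | (12.5 + 1.8)/128 = 11.2% |
| 6 | (12.2 + 1.8)/128 = 10.9% | (12.2 + 3.6)/128 = 12.3% |
| 13 | (11.5 + 3.9)/128 = 12.0% | (11.5 + 7.8)/128 = 15.1% |

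In counts: if 6 ineligible patients have 2 of 12 SADRs, the plan reports 10/122 = 8.2% where the all-treated figure is 12/128 = 9.4%.

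**3. Direction.** The reported rate minus the all-treated rate is (0.10 − r) × x / 128. It is zero when r = 10%, whatever x is. It is positive when r is below 10%: with r = 5% and x = 13 the all-treated rate is (11.5 + 0.65)/128 = 9.5%, so the plan would overstate it.

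**4. Undosed patients.** Assume 128 eligible enrolled patients, of whom m are never dosed, and an event rate of 20% in those treated. The FAS percentage is 0.20 × (128 − m)/128.

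- m = 3: 25.0/128 = 19.5%
- m = 6: 24.4/128 = 19.1%
- m = 13: 23.0/128 = 18.0%

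This dilution concerns the n (%) tables. In the EAIR, SAP 9.2 starts the clock at treatment onset for a patient with events, so time at risk has no defined start for a patient never dosed.

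**5. Both together.** Assume 128 enrolled, 6 treated but ineligible with a 50% event rate, 6 eligible but undosed, and 20% in the 116 eligible treated patients. The FAS gives 23.2/122 = 19.0%. The treated patients give (23.2 + 3.0)/122 = 21.5%.

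**The case against.** The strongest defence has four parts.

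**The events are not lost.** Protocol 13.2 requires serious adverse reactions and fatal events to be reported within 24 hours and non-serious reactions within 7 calendar days, with no condition on later eligibility. SAP 9.2 plans a listing of all reported adverse events with patient and centre identifiers, and SAP 5.1 tabulates non-eligible patients by site. This stands. A reader might infer that reactions in ineligible patients vanish from the study; the documents do not support that. But the population of the listing is not stated, the exclusion rule leaves it open, and the deviation listing in SAP 5.2 carries only site, patient number and deviation. Neither expedited reports nor a listing gives a rate.

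**No bias has been shown.** This also stands. A reader might infer that exclusion is tied to risk, so that reported rates must lean low. Only the contraindication criterion suggests this directly. Others, such as ability to complete the questionnaires, have no stated link to risk. Patients who started afatinib more than 7 days before enrolment are also ineligible and could push the other way: Protocol 11.3.3 places the usual onset of diarrhoea in the first two weeks, and collection begins only at consent. At 10% with n = 128, the 95% half-width is 1.96 × √(0.09/128) = 5.2 percentage points, wider than the shift of 0.5 to 2.3 points seen with 3 to 6 ineligible patients.

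**Undosed patients may not exist.** SAP 2.3 describes each participant as being treated with afatinib. However, the FAS wording does not require it, and Protocol 11.10 speaks of patients whose treatment precedes enrolment as only some of those enrolled. The withdrawal criteria (Protocol 11.2.4.3) were not in the text available for this review, so any rule there on undosed patients could not be checked.

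**Safety is not an objective.** The study is descriptive, safety is in neither the primary nor the secondary objectives, and the primary result is untouched. This limits the weight of the point. It does not justify a safety population defined by something other than exposure.

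**Conclusion.** The point holds as a defect in the definition of the safety population. Followed as written, both documents remove afatinib-exposed patients found ineligible from the safety tables and EAIRs, and keep any eligible undosed patient in the n (%) denominators. The two documents agree with each other, so this is a design choice and not a contradiction.

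Size and direction are unknown. The effect is zero if no such patients occur, or if all enrolled patients are dosed and ineligible patients have the same event rate as eligible ones. It would be wrong to infer that it is zero only when every enrolled patient is eligible and dosed. Rates are understated if ineligible patients have a higher event rate. The illustration of 10.5-15.1% against 10% rests wholly on assumed counts (3 to 13 ineligible) and assumed risks (10%, and 30-60% in the ineligible). It is not evidence of a downward bias in this study.

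This should be fixed before database lock, but it does not threaten the primary analysis.

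**What to change.** In Protocol 11.8.1 and SAP 3.5:

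- Define a Safety Set of all enrolled patients with valid informed consent and at least one documented afatinib dose, regardless of the other eligibility criteria.
- Use it for SAP 9.1-9.3 (exposure, adverse events, EAIRs, vital signs), and align Protocol 11.8.5.
- Limit the exclusion of erroneously enrolled patients to the effectiveness and patient-reported outcome analyses.

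In SAP 9.2:

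- State the population of the adverse event listing.
- List fatal events between consent and first dose separately.
- For patients who started afatinib before consent, count EAIR time at risk only from the start of adverse event collection. Otherwise the new set would add time in which events could not have been recorded.

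The cost is wording in two documents and one population flag. The data are already collected and the sample size does not change. Safety and effectiveness tables may then have different denominators. A few patients with concurrent investigational drugs may have confounded attribution, which can be flagged.
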